# Statistical Analysis Plan

## SYLVI- study

### Power Calculation

The power calculation is based on our previous study showing that the Matsuda index decreases 23% (from 7.3 [ $\pm 2.9$ ] to 5.6 [ $\pm 2.8$ ]) during the use of COC containing EE for nine weeks 1. COCs containing EV have not been shown to affect glucose tolerance 2–4. Therefore we hypothesize that the Matsuda index decreases significantly in the EE group but remains unaffected in the EV and DNG-only groups 2. Based on this previous data, the effect size was estimated to be  $f = 0.25$  ( $f$  as defined by Cohen). With the significance level set at  $<0.05$  (the risk of a-error) and the desired power at 0.8 (risk of 1-b error), 16 participants were required in each of the three groups. We aimed to enroll 60 women to allow for possible discontinuation or loss during follow-up. We used the G\*Power software ([www.gpower.hhu.de](http://www.gpower.hhu.de)) for the sample size calculation.

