## Statistical Analysis

We will use IBM SPSS version 25 and 27 and Prism 9 (Graphpad) for Mac iOS for all statistical calculations. The significance level will be set at  $<0.05$ . Summarized data will be expressed as mean ( $\pm$ SD or 95%CI) or medians (ranges) as appropriate. The change from baseline will be described as mean (95%) or median (range) as applicable. Shapiro-Wilks test will test the normality of the data, and skewed variables will be log-transformed if needed. Comparisons of baseline demographic characteristics among the three groups will be performed using one-way analysis of variance (ANOVA). Repeated measures will be analyzed with one-way multiple measures ANOVA (analysis within-group) and two-way multiple measures ANOVA (analysis between groups) or the hierachal linear mixed model. Corrections for multiplicity (Bonferroni) will be applied. Parametric and nonparametric counterparts will be used to compare the within-group changes for secondary outcomes. The between-group changes from baseline will be analyzed by ANOVA or Kruskal-Wallis test with post hoc tests.

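### The stated 80% power at 16 women per group does not follow from the plan's own Matsuda figures for the three-group comparison

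*SAP*

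**What the plan says.** The SAP's Power Calculation cites a previous study in which the Matsuda index under EE went from 7.3 (SD 2.9) to 5.6 (SD 2.8), a fall of 23%. The hypothesis is that "the Matsuda index decreases significantly in the EE group but remains unaffected in the EV and DNG-only groups". The text continues "Based on this previous data, the effect size was estimated to be" 0.25 on Cohen's scale. With alpha 0.05 and power 0.8 it concludes that "16 participants were required in each of the three groups". Sixty women are to be enrolled to allow for losses. The software is named (G*Power), but the test, the number of measurements and the correlation between measurements are not.

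The Statistical Analysis section gives two between-group analyses that could be meant. One is a "two-way multiple measures ANOVA (analysis between groups"), with a mixed model as an alternative. The other is stated as "The between-group changes from baseline will be analyzed by ANOVA or Kruskal-Wallis test with post hoc tests".

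**The concern.** The section presents a chain: cited means and SDs, then f = 0.25, then 16 per group at 80% power. Cohen's f has no fixed meaning until the test is named. The same three trajectories give different values of f for a one-way comparison, for a group-by-time interaction and for an analysis of change scores, and each value needs its own sample-size formula. If f comes from one scale and is entered on another, the resulting power does not apply to the cited effect.

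This matters for interpretation. The hypothesis expects a change under EE and none under EV or DNG, so non-significant results will be read as informative. A reader who trusts 80% power would give a non-significant between-group result more weight than the cited data justify.

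**Working it through.** **Inputs from the SAP.** EE 7.3 (SD 2.9) to 5.6 (SD 2.8), a fall of 1.7; no change in EV and DNG; three equal groups; alpha 0.05; N = 48 (16 per group) or 60 (20 per group). The average-variance SD is √[(2.9² + 2.8²)/2] = 2.85. The SAP gives no correlation ρ and no number of visits m, so both are assumptions below. Power is from the noncentral F distribution.

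**1. Reproducing 16 per group from f = 0.25**

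- *One-way ANOVA:* λ = f²N, df 2 and N − 3. At N = 48, λ = 0.0625 × 48 = 3.0 and power is 30%. At N = 60 it is 37%. Reaching 80% takes N = 159, or 53 per group. This reading does not give 16.
- *Group-by-time interaction (G*Power's default effect-size option):* λ = f²Nm/(1 − ρ), df 2(m − 1) and (N − 3)(m − 1). This gives N = 48 when ρ is about 0.42–0.45 with m = 2, 0.3 with m = 3, or 0.2 with m = 4. The stated figure can therefore be reached, but only with an unstated ρ and m.

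**2. The interaction f from the plan's own scenario**

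- f = SD of (1, 0, 0) across groups × SD of the EE means over visits / 2.85.
- The first factor is √(2/9) = 0.471. With two visits the second is 1.7/2 = 0.85.
- f = 0.471 × 0.85 / 2.85 = 0.14, not 0.25.
- If the EE fall never exceeds 1.7 units, the SD over visits cannot exceed 0.85, so about 0.141 is the ceiling for any number of visits.
- Conversely, f = 0.25 with two visits implies an EE-only fall of 0.25 × 2.85 / (0.471 × 0.5) = 3.0 units, or 41% of 7.3. The cited fall is 1.7 units, or 23%.

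**3. Power at N = 48 for the plan's scenario, at the settings that turn f = 0.25 into 48 women**

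| Visits | ρ | Power with f = 0.25 | Power with the plan's scenario |
|---|---|---|---|
| 2 | 0.42 | 80% | 33% |
| 2 | 0.45 | 82% | 34% |
| 3 | 0.3 | 81% | at most 31% |
| 4 | 0.2 | 82% | at most about 31% |

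**4. Power of the change-score ANOVA (two visits)**

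SD of change = √(2.9² + 2.8² − 2ρ × 2.9 × 2.8); f = 0.471 × 1.7 / SD of change; λ = f²N. For example, at ρ = 0.5 the SD of change is 2.85, f = 0.281, λ = 0.281² × 48 = 3.8 and power is 37%. The two-visit interaction test gives the same power to within rounding.

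| ρ | Power, 16 per group | Power, 20 per group | EE-only fall detectable with 80% power, 16 per group |
|---|---|---|---|
| 0 | 20% | 25% | – |
| 0.3 | 28% | 34% | 3.3 |
| 0.5 | 37% | 46% | 2.8 |
| 0.7 | 58% | 69% | 2.2 |
| 0.8 | 76% | 86% | 1.8 |
| 0.82 | 81% | 90% | – |

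Power reaches 80% at ρ = 0.816 with 16 per group, and at 0.77 if all 60 women complete.

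**5. Can one correlation support both steps?** At ρ = 0.82 with two visits, f = 0.25 under the default option would have required only 18 women in total. A correlation high enough for the cited effect to give 80% therefore cannot be the one that produced 48.

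**6. Within-EE reading.** A paired test in 16 EE women reaches 80% at ρ of about 0.68. At ρ = 0.7 it has 82% power, against 58% for the three-group test.

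**The case against.** The strongest reply is that f = 0.25 may well come from the cited data on another scale. Follow-up means of 5.6, 7.3 and 7.3 with SD 2.85 give a one-way f of 0.28, and the change-score f equals 0.25 at ρ of about 0.37. This stands as a point about where the chain breaks: on those scales the fault lies in the step from f to 16, not in f itself. It does not rescue the 80%, because f = 0.25 on either scale gives 30% power with 48 women.

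Second, the section never says that the 80% refers to the three-group comparison. The hypothesis is worded partly within groups, and a within-group analysis is planned. That reading cannot be excluded, and it needs a lower correlation (0.68). It would, however, power only the EE fall, and a requirement set for each of three groups with Cohen's f reads more naturally as a three-group calculation.

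Third, the 0.82 threshold belongs to two visits, a 2-df test and 16 completers per group without baseline adjustment. Other choices lower it somewhat: 0.77 if all 60 complete, 0.79 for ANCOVA at 16 per group, and 0.77 for a 1-df contrast of EE against the other two groups. The ANCOVA and the contrast are not named in the SAP. All of these are still high correlations.

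Finally, the document does not say which correlations are plausible, and the protocol, which is not at hand, may give the visit schedule. The result must therefore be stated as a range. The absence of these details is not the complaint.

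**Conclusion.** The point holds. For the comparison of the three groups, the cited Matsuda figures do not deliver 80% power with 16 women per group unless the baseline to follow-up correlation is about 0.82 or higher, assuming two visits and a change-score or group-by-time test. Over assumed correlations of 0.3 to 0.7, power is 28% to 58%. At the two-visit interaction settings that reproduce the stated 48 women, it is about one third. On that interaction scale the plan's scenario corresponds to f of about 0.14, and entering 0.25 assumes a fall of 3.0 units in place of the cited 1.7.

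The fault is a stated power that does not follow from its own inputs. A correlation above 0.82 cannot be ruled out, but it would not explain how 48 was obtained. If the calculation was for the fall within EE alone, 80% is reached at about 0.68, but that is not power for the between-group comparison.

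**What to change.** Revise the Power Calculation section of the SAP and leave enrolment unchanged:

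1. Name the test that the calculation is for, with the number of measurements and the correlation used.
2. Derive f on that test's scale from the cited values: 7.3 to 5.6 under EE, no change under EV and DNG, SDs 2.9 and 2.8.
3. Replace the 80% statement by between-group power over a stated range of correlations. With two visits and 16 per group this is 28%, 37%, 58% and 76% at 0.3, 0.5, 0.7 and 0.8. Alternatively, give the smallest EE-only fall detectable with 80% power: 3.3, 2.8, 2.2 and 1.8 units at the same correlations.
4. If 16 was intended for the change within EE, say so, and do not present it as power for the three-group comparison.

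The cost is a change of wording only: no extra participants and no change of analysis. The drawback is a less favourable stated power.

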### Randomization

The study subjects will be allocated to three parallel treatment groups by randomization in a 1:1:1 ratio and blocks of six. A statistician will produce the randomization list using a web-based randomizer ([www.sealedenvelope.com](http://www.sealedenvelope.com)). Two research nurses will allocate the women to the treatment groups after established eligibility.

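### The SAP fixes one constant block size of six; if past assignments are known and pooled, one allocation in five can be foreseen with certainty, and varying the sizes would cut that cheaply

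*SAP*

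**What the plan says.** The Randomization section of the SAP states that the women will be "allocated to three parallel treatment groups by randomization in a 1:1:1 ratio and blocks of six". With three arms at equal ratio, that is two women per arm in every block. It describes a single list: "A statistician will produce the randomization list using a web-based randomizer". No stratification and no second block size are mentioned. On who performs the allocation: "Two research nurses will allocate the women to the treatment groups after established eligibility".

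The Power Calculation section sets the scale: "We aimed to enroll 60 women to allow for possible discontinuation or loss during follow-up". Sixty women make ten complete blocks of six.

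The SAP does not state whether treatment is open or masked, whether the nurses learn which treatment they assign, whether they know the block size, whether they share a record of past assignments, or how the list is concealed.

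**The concern.** With one constant block size, the composition of every block is known to anyone who knows that size. A person who also knows the assignments made so far can count through the block and work out its end. Concealing the list does not prevent this, because the end of the block follows from what has already been assigned.

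What is at stake is selection at entry. If the next arm can be foreseen, it can affect when, or whether, an eligible woman is entered. The trial is small (16 per group required, 60 planned). The Matsuda index behind the power calculation varies widely between women: the SAP cites a baseline of 7.3 with an SD of 2.9. The Statistical Analysis section names no adjustment for baseline covariates, so a shift in who enters which arm would not clearly be corrected in the analysis.

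**Working it through.** **Inputs.** Three arms, 1:1:1, block size 6, one list, two allocating nurses (SAP, Randomization); 60 women (SAP, Power Calculation). The SAP gives no predictability figure to reproduce. What the nurses know is an assumption, so three cases are shown.

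**Case A: block size and all past assignments known and pooled.** A block has 6!/(2!·2!·2!) = 90 equally likely orderings.

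*Fully determined allocations.* The sixth is always determined. The fifth is determined when the last two women fall in the same arm, with probability 1/5. Earlier positions never are. Expected number per block: 1 + 1/5 = 1.2. Share: 1.2/6 = 20%. Over ten blocks: 12 of 60.

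*At least one arm excluded.* Positions 1 and 2: never. Position 3: first two alike, 1/5. Position 4: some arm used up within the first three, 3 × 4/20 = 3/5. Positions 5 and 6: always. Sum: 0.2 + 0.6 + 1 + 1 = 2.8. Share: 2.8/6 = 46.7%.

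*Best guess (the arm with most places left).*

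| Position | Probability of a correct guess |
|---|---|
| 1 | 1/3 |
| 2 | 2/5 |
| 3 | 1/2 |
| 4 | (2/5)(1/3) + (3/5)(2/3) = 8/15 |
| 5 | (1/5)(1) + (4/5)(1/2) = 3/5 |
| 6 | 1 |

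Sum: 101/30 = 3.367. Average: 3.367/6 = 56.1%, against 33.3% by chance. Enumeration of all 90 orderings gives the same three figures.

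**Case B: each nurse knows only her own assignments.** Assume each woman goes to either nurse with probability 1/2 and block boundaries are known. Certainty then requires that the allocating nurse personally made all four assignments that filled two arms, with probability (1/2)^4 = 1/16. Fifth position: 1/5 × 1/16 = 1/80. Sixth position: 1/16. Sum: 6/80 = 0.075 per block. Share: 0.075/6 = 1.25%, under one woman in 60. A simulation of 200,000 blocks gave 1.2%.

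**Case C: assignments masked from the nurses.** No allocation is determined.

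**With varying sizes.** The comparison is with Case A. The guesser knows every past assignment and which sizes are possible, and updates the probability of each block boundary (simulation over 60 allocations).

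| Design | Determined | At least one arm excluded | Best guess right |
|---|---|---|---|
| Constant 6 | 20.0% (12 of 60) | 46.7% | 56.1% |
| 6 and 9, each size drawn independently | about 5% (3 of 60) | about 14% | about 54% |
| Four of each in random order, composition known | about 7% (4 to 5 of 60) | about 19% | about 54% |

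Four blocks of each size make 4 × 6 + 4 × 9 = 60 women, 20 per arm.

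**The case against.** The strongest case against is that a block size of six is not an error in itself. It does harm only if past assignments are visible, and this SAP cannot tell us that. Concealment and masking usually belong in the protocol, so their absence here is no fault. A reader might infer from the Randomization section that the nurses see each treatment they assign, and hence that one allocation in five is in fact open to manipulation. The SAP does not support that: it says only that two nurses allocate. The 20% needs a known block size, tracked boundaries, visible treatments and pooled records, all at once. Nor does stating the size in the SAP show that the nurses had it during enrolment.

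Two further points have weight. Allocation follows established eligibility, which narrows the scope for selection. And varying the sizes hardly changes average guessing success, 56% against about 54%.

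All of this stands against a categorical claim. It does not remove the point. The constant size is a choice made in this document, and concealing the list does not cure it if assignments become visible. Checking eligibility first does not stop a foreseeable next arm from affecting when a woman is entered. The gain from varying sizes lies in certainty and in excluded arms, and certainty is what most readily allows an entry to be timed.

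**Conclusion.** The point holds conditionally, as a minor improvement. The determined share is 20% (12 of 60) if the block size and all past assignments are known and pooled, about 1% if each nurse knows only her own (random half split), and nil under masking. The SAP does not show which case applies. The arithmetic of the pooled case is exact; the 1% rests on the assumed split between the nurses.

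It does not follow that selection occurred, or that concealment was inadequate. Nothing in the SAP shows an imbalance in any baseline trait.

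**What to change.** Have the statistician generate the list, or the part not yet used, in randomly ordered blocks of varying size, for example 6 and 9. The sizes should not be stated in the SAP, since that would undo part of the benefit. Suggested wording:

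> The statistician will generate the list in randomly ordered blocks of varying size. Block sizes and their order will be kept in a separate document, withheld from the nurses and investigators until enrolment is complete.

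Also confirm in the protocol whether the nurses can see past assignments.

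The cost is one change of wording and a regenerated list. The statistical price is slightly more possible imbalance if enrolment stops mid-block: two arms can differ by at most 3 within a block of nine, against 2 within a block of six. If past assignments are fully masked, the change gains nothing and costs almost nothing. If enrolment is already complete, report instead the block size used and who knew the past assignments.

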## Statistical Analysis

We will use IBM SPSS version 25 and 27 and Prism 9 (Graphpad) for Mac iOS for all statistical calculations. The significance level will be set at  $<0.05$ . Summarized data will be expressed as mean ( $\pm$ SD or 95%CI) or medians (ranges) as appropriate. The change from baseline will be described as mean (95%) or median (range) as applicable. Shapiro-Wilks test will test the normality of the data, and skewed variables will be log-transformed if needed. Comparisons of baseline demographic characteristics among the three groups will be performed using one-way analysis of variance (ANOVA). Repeated measures will be analyzed with one-way multiple measures ANOVA (analysis within-group) and two-way multiple measures ANOVA (analysis between groups) or the hierachal linear mixed model. Corrections for multiplicity (Bonferroni) will be applied. Parametric and nonparametric counterparts will be used to compare the within-group changes for secondary outcomes. The between-group changes from baseline will be analyzed by ANOVA or Kruskal-Wallis test with post hoc tests.

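### The SAP offers RM ANOVA or a mixed model for the between-group repeated measures without saying which one decides the Matsuda result, or whether it adjusts for baseline

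*SAP*

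**What the plan says.** The Power Calculation section builds the trial on the Matsuda index. In the sponsor's previous study it fell from 7.3 (SD 2.9) to 5.6 (SD 2.8) on an EE-containing pill. The hypothesis is that "the Matsuda index decreases significantly in the EE group but remains unaffected in the EV and DNG-only groups". The SAP does not itself label this outcome primary. The requirement is 16 women per group, and loss is expected: "We aimed to enroll 60 women to allow for possible discontinuation or loss during follow-up".

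For repeated measures, the Statistical Analysis section gives one-way RM ANOVA within groups and, between groups, "two-way multiple measures ANOVA (analysis between groups) or the hierachal linear mixed model". Three further sentences bear on the point:

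- "Corrections for multiplicity (Bonferroni) will be applied". The family of tests is not defined.
- For secondary outcomes, changes inside each group are to be tested by parametric or nonparametric methods.
- "The between-group changes from baseline will be analyzed by ANOVA or Kruskal-Wallis test with post hoc tests". This follows the sentence on secondary outcomes, so it is unclear whether it also covers the Matsuda index.

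The Shapiro-Wilk and log-transformation sentence deals with normality. It does not choose between the two repeated-measures methods.

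**The concern.** Each listed method holds its error rate if it is fixed in advance. Joined by an unqualified alternative, they let the choice be made once the results are known. The choice also settles who is analysed. Conventional RM ANOVA drops a woman with an incomplete row, whereas a mixed model keeps her observed visits. (Listwise deletion is the usual convention and is assumed here; the SAP does not state it.)

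The label of a mixed model is also not a full specification. Covariance structure, handling of baseline and the contrast tested are all open. Baseline handling matters most for precision, and the SAP does not mention it.

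**Working it through.** **1. The plan's own figure.** For a group-by-visit interaction, λ = f²·N·m/(1−ρ), with df (k−1)(m−1) and (N−k)(m−1). From the SAP: f = 0.25, α = 0.05, k = 3, N = 48. The number of measurements m and the correlation ρ are not given.

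- m = 2, ρ = 0.45: λ = 0.0625 × 48 × 2 / 0.55 = 10.91, power 82%.
- m = 3, ρ = 0.3: λ = 0.0625 × 48 × 3 / 0.7 = 12.86, power 81%.

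Sixteen per group is therefore attainable under repeated-measures assumptions but cannot be uniquely reproduced. On enrolment, 48/60 = 0.80, so the target leaves room for 20% loss. The SAP gives no rate.

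**2. Assumptions for the illustrations.** There are 20 women per arm (60/3), SD 2.85 (midpoint of 2.9 and 2.8) and ρ = 0.5 / 0.7. EE falls by 7.3 − 5.6 = 1.7 at the last visit, with half of that at an interim visit if there are three, and the other arms do not change. Visits, correlation and loss pattern are assumed.

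**3. Complete data.** RM ANOVA and a mixed model with free group baselines give the same group-by-visit test. With two visits this holds under compound symmetry or unstructured covariance. With three or more it holds only under compound symmetry. Simulated disagreement at p < 0.05 between RM ANOVA and the compound-symmetric model was 0%.

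**4. Four of 20 per arm missing the last visit at random.** This compares RM ANOVA on completers with a compound-symmetric, free-baseline REML model on all observed data (10,000 trials per case; values are ρ = 0.5 / 0.7):

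| | Two visits | Three visits |
|---|---|---|
| Disagree, null | 2.0% / 1.7% | 3.5% / 3.3% |
| Disagree, with effect | 6.5% / 6.2% | 9.6% / 10.2% |
| Type I error if either may be reported | 6.0% / 5.7% | 6.6% / 6.7% |
| Power, RM ANOVA | 37.2% / 57.3% | 28.6% / 48.3% |
| Power, mixed model | 38.9% / 59.0% | 31.1% / 51.2% |

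Keeping women with a missed visit adds 1.7 points (38.9 − 37.2 and 59.0 − 57.3) with two visits. With three it adds 2.5 and 2.9 points (31.1 − 28.6; 51.2 − 48.3). A separate 1,000-run simulation with three visits and ρ = 0.5 gave 3.6% null disagreement, 9.0% with the effect and 6.6% type I error.

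**5. Baseline adjustment, two complete visits.** The between-group sum of squares is 20 × 1.7² × 2/3 = 38.53.

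- RM ANOVA (equivalent to ANOVA on change): error variance 2 × 2.85² × (1−ρ) = 8.12 / 4.87, λ = 4.74 / 7.91, df 2 and 57, power 46% / 69%.
- Same omnibus test with baseline as covariate: error variance 2.85² × (1−ρ²) = 6.09 / 4.14, λ = 6.33 / 9.30, df 2 and 56, power 58% / 76%.

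The gain is about 12 / 7 points. Replacing the omnibus test by the two adjusted EE contrasts, each at 0.025, gives 61% / 78%.

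**6. Error rate of a pre-named model.** This is the familywise rate for the two last-visit contrasts, each at 0.025, with unstructured covariance and a common baseline mean. It was 4.5–4.8% with Kenward-Roger degrees of freedom and 5.1–5.6% with Satterthwaite.

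**The case against.** The strongest reply is that this is close to missing detail. In standard form the two methods agree with complete data. Under the assumed loss, type I error reaches only about 6–7%, and only if someone runs both and reports the better one. The protocol is not shown and may name the primary endpoint, the visits and the analysis. All of that stands, and it limits the point to a modest gap in this document's own text. It does not remove the gap, because nothing in the SAP chooses between the methods.

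Three stronger readings are tempting and not supported:

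- **That the choice swings the result in up to 30% of trials.** Comparing the omnibus RM ANOVA with baseline-adjusted last-visit contrasts, at two or three visits with no loss, gives disagreement in 13.0–29.7% of trials with the effect. That comparison also changes the hypothesis and the adjustment, and the SAP names neither those contrasts nor a baseline constraint. It does not measure the alternative the SAP offers.
- **That choosing RM ANOVA over a mixed model costs much power.** Keeping incomplete cases is worth 1.7–2.9 points. The larger gain comes from baseline adjustment, which ANCOVA on completers could largely supply, and from focused contrasts.
- **That powers of 46% / 69% show the sample size to be wrong.** They rest on an assumed effect pattern and correlation. The SAP does not state the test family, number of measurements or correlation behind 16 per group, and that figure is attainable.

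**Conclusion.** The point holds as a modest pre-specification gap with a worthwhile improvement attached. The SAP does not say which between-group method decides the Matsuda result or whether it adjusts for baseline. The two listed methods, in standard form, diverge only when visits are missed or, from three visits on, when the covariance is not compound-symmetric. At an assumed 20% loss of the last visit the consequence is the 2–4% and 6–10% disagreement and 6–7% type I error shown above. Listwise deletion, 20 per arm, SD 2.85, correlation 0.5–0.7 and two or three visits are all assumptions. This is not a numerical error and does not make the trial invalid.

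**What to change.** In the Statistical Analysis section, name one primary between-group analysis for the Matsuda index before the data are analysed. Preferred content:

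- a linear mixed model (REML, unstructured covariance) on all randomised women with available data;
- a common baseline mean across groups, or baseline as covariate;
- one stated small-sample degrees-of-freedom method;
- the between-group contrasts at the last scheduled measurement, and the Bonferroni family they form (for example EE–EV and EE–DNG, each at 0.025), with matching confidence intervals.

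Label RM ANOVA as a sensitivity analysis, and likewise the change-score ANOVA or Kruskal-Wallis test if it is meant to cover this outcome. Naming RM ANOVA as the single primary analysis would also close the pre-specification gap, but without the gain from baseline adjustment.

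The cost is SAP wording only, with no change to visits, sample size or data collected. The downsides are slightly more modelling work, reliance on a covariance structure in a small sample, and familywise error of about 5.1–5.6% if Satterthwaite degrees of freedom are used.

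### Optional improvement, not an error: if Bonferroni is meant for the three between-group comparisons of Matsuda change at one time contrast, a closed procedure holds the same 5% with more power

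*SAP*

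**What the plan says.** The Statistical Analysis section of the SAP states: "Corrections for multiplicity (Bonferroni) will be applied". It does not say which tests are counted. The sentence stands directly after the one on repeated measures, which plans "one-way multiple measures ANOVA (analysis within-group) and two-way multiple measures ANOVA (analysis between groups") or a hierarchical mixed model. A later sentence reads: "The between-group changes from baseline will be analyzed by ANOVA or Kruskal-Wallis test with post hoc tests". It names no post hoc test and does not say whether the omnibus test must be significant first.

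The Power Calculation section is built on the Matsuda index. It expects that the index "decreases significantly in the EE group but remains unaffected in the EV and DNG-only groups". It states that "16 participants were required in each of the three groups", and adds: "We aimed to enroll 60 women to allow for possible discontinuation or loss during follow-up".

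**The concern.** The expected pattern makes EE-EV and EE-DNG the comparisons that separate EE from the other two arms. A natural reading of the plan is that the three pairwise comparisons of change would each be tested at 0.05/3 = 0.0167. That is a valid rule, but it ignores a logical link between the three hypotheses and so gives up power that a change of wording would recover. In a trial that needs only 16 women per arm, the loss on EE-EV equals about three women per arm.

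**Working it through.** **Inputs from the SAP.** Three arms, 1:1:1 (Randomization). Level 0.05 (Statistical Analysis; two-sided tests assumed). Matsuda 7.3 (SD 2.9) falling to 5.6 (SD 2.8) with EE, no change with EV or DNG; 16 per group, 60 enrolled (Power Calculation).

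**Assumed.** The before-after correlation ρ is not in the SAP and is taken as 0.3 to 0.8. Changes are normal with the same SD in each arm.

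**The plan's own figure.** The 16 per group does not come from pairwise tests. With f = 0.25, a one-way ANOVA needs 53 per group. A repeated-measures interaction with three measurements and correlation 0.3 gives 16, but the SAP states neither setting. Here 16 is taken as given; nothing below depends on how it was derived.

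**Why 0.0167 throughout is stricter than needed.** With three means, either all are equal, or exactly one pair is equal, or none is.
- All equal: a false rejection requires passing the first step. That is bounded by 5% if the smallest p-value must be at most 0.0167, and equally if an omnibus test must be significant at 0.05.
- Exactly one pair equal: only that pair can be falsely rejected, and testing it at 0.05 bounds the error by 5%.
- None equal: no false rejection is possible.

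So after either first step each remaining pair can be tested at 0.05. Every Bonferroni rejection has p at or below 0.0167, so Shaffer's step-down makes it too. This reasoning does not depend on ρ.

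**Size.** The SD of change is √(2.9² + 2.8² − 2ρ·2.9·2.8) = √(16.25 − 16.24ρ), which is 3.37, 2.85, 2.21 and 1.80 at ρ = 0.3, 0.5, 0.7 and 0.8. For EE-EV the noncentrality is 1.7/(SD·√(2/16)). The Bonferroni critical value on 45 df is 2.487, giving power 0.155, 0.223, 0.387 and 0.573. Simulation with pooled-variance t tests agrees and supplies the other columns.

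EE-EV power, 16 per group:

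| ρ | Bonferroni | (a) Shaffer | (b) Omnibus gate |
|---|---|---|---|
| 0.3 | 16% | 19% | 21% |
| 0.5 | 22% | 27% | 29% |
| 0.7 | 39% | 46% | 49% |
| 0.8 | 57% | 65% | 68% |

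Other results at 16 per group, for ρ = 0.5, 0.7, 0.8:
- Both EE contrasts rejected: Bonferroni 11, 23, 42%; (a) 19, 37, 58%; (b) 22, 40, 60%. At ρ = 0.3, Bonferroni gives 6.3% and (a) 12.5%.
- Any rejection: 34, 54, 73% with Bonferroni and with (a); 37, 58, 76% with (b).
- Bonferroni rejections lost: none with (a); about 0.3-0.4% of trials with (b).
- EV-DNG falsely rejected: Bonferroni 1.7%; (a) 3.9, 4.5, 4.8%.

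Familywise error at 16 per group: with all arms equal, 4.3% for Bonferroni and (a), 5.0% for (b); with EE far apart, 1.7% for Bonferroni and 5.0% for (a) and (b).

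At 20 per group (60/3, no losses) and ρ = 0.5 to 0.8, EE-EV power rises from 29-69% to 34-77% with (a). At each of ρ = 0.5, 0.6, 0.7 and 0.8, Bonferroni needs 19 per group to match (a) at 16, and 24 to match (a) at 20.

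**Other scales.** The SAP also says "skewed variables will be log-transformed if needed" and allows rank tests. On a log scale (lognormal data with the SAP's means and SDs), EE-EV power at ρ = 0.5 to 0.8 goes from 38-79% to 44-86% with (a). With pairwise Mann-Whitney tests it goes from 18-50% to 23-59%.

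**The case against.** The strongest reply is that nothing here is wrong: Bonferroni is valid, and preferring another valid procedure is a matter of choice. That stands, and it is why this is offered as optional.

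Second, a reader might infer that the SAP assigns Bonferroni to these three pairs. It does not. The sentence follows the repeated-measures sentence, the Matsuda index is not named in that section, and the expected pattern can also be read as a set of within-group statements. The point is therefore conditional.

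Third, the omnibus test already in the plan could serve as the gate, and under the expected pattern it does slightly better than Shaffer's step-down. This is right. The SAP does not say that the omnibus test gates the pairs or that the pairs are then tested at 0.05, so it belongs among the options and cannot be taken as already planned.

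Fourth, the gain depends on an assumed correlation: at 0.3, EE-EV rises only from 16% to 19% with (a). This stands, and the range above includes it.

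Fifth, there are costs. More false positives are allowed on EV-DNG, the pair expected not to differ, and matching simultaneous intervals are lost. At 16 per group Bonferroni intervals are 23% wider than unadjusted ones (2.487/2.014 = 1.235). The plan says "The change from baseline will be described as mean (95%) or median (range) as applicable", which is not labelled simultaneous, so little that was promised would be lost. A sponsor who wants matched intervals may still reasonably keep Bonferroni.

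**Conclusion.** This is an optional, cheap improvement. It applies only if Bonferroni is used for the three pairwise comparisons of Matsuda change at one time contrast. In that case, at 16 per group and ρ from 0.3 to 0.8, EE-EV power rises by about 3 to 8 percentage points with (a) and 5 to 11 with (b). The error bound for both options, and the fact that (a) never rejects less than Bonferroni, do not rest on the assumed correlation; the power figures do. They also assume the SAP's EE effect and no change with EV or DNG.

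Three stronger readings are not supported. Bonferroni is not an error and does not contradict the power paragraph. The SAP does not define success as showing both EE contrasts, so the larger gain there is not the main result. Nor does the change rescue the power of a single contrast: on the raw scale at 16 per group, EE-EV stays below 80% under all three rules.

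**What to change.** For the comparisons EE-EV, EE-DNG and EV-DNG on change in the Matsuda index at one named time contrast, state one of these in place of Bonferroni before the data are seen:

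- **(a) Shaffer's step-down.** If the smallest of the three p-values is at most 0.0167, test the other two pairs at 0.05 each; otherwise declare no pair different.
- **(b) Omnibus gate.** If the omnibus test of change at that time contrast is significant at 0.05, test each pair at 0.05; otherwise declare no pair different.

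Option (a) never loses a Bonferroni rejection. Option (b) has slightly more power under the expected pattern but loses a few isolated ones. If rank tests are used, the pairs should be compared by pairwise Mann-Whitney tests whose null is equality of distributions.

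These thresholds do not carry over to several visits, within-group tests or other outcomes; Bonferroni stays there. The change needs SAP wording only. The sponsor should weigh the two downsides: no simultaneous confidence intervals that match the tests, and an EV-DNG false-positive rate of up to 5%, against about 1.7% with Bonferroni, when EE differs.
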